4. RESEARCH DESIGN AND METHODS

4.1 Design

We will conduct a single-center randomized, controlled, double-blinded trial to determine the effect of amantadine administration in patients resuscitated from cardiac arrest who remain comatose at hospital day 3. The primary outcome will be the rate of awakening (defined as following commands) during hospitalization.

4.2 Recruitment and Informed Consent:

The Post-Cardiac Arrest Service treats over 90% of patients successfully resuscitated from cardiac arrest at UPMC Presbyterian Hospital, ensuring that the PI will care for all potential candidates as part of his clinical duties. Potential subjects who remain comatose for 48 hours will be unable to provide informed consent. Therefore, the investigators will approach family or legally authorized representatives to provide consent as a proxy for the subject. The investigators will already have a relationship with these proxies, and we have previously recruited 50% of potentially eligible subjects into studies in this setting. [30, 31]

4.3 Inclusion and Exclusion Criteria are listed in **Table 2**.

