4.15 Statistical Analysis

4.15.a Random Assignment

Those eligible for the study will be randomly assigned with equal probability to the experimental condition (amantadine) or the control condition (placebo). Random assignment will be stratified by cardiac arrest category (PCAC) and presence of malignant EEG patterns (only in those with PCAC II), resulting in four strata: PCAC IV, PCAC III, PCAC II with malignant EEG patterns, and PCAC II without malignant EEG patterns. Survival markedly differs between these strata. [Section 3.C.1.b]

To maximize the probability of a balanced design, assignments will occur in block of two and four within each stratum. To ensure that the research team will be masked to the next treatment assignment, the size of the block will be randomly generated.

Random assignment will occur through the University of Pittsburgh Investigational Drug Service (IDS). Study staff will contact the IDS pharmacist, provide the necessary information (e.g., stratum) and the random assignment will be delivered. Given the volume of clinical studies at the University of Pittsburgh, IDS pharmacy medications and randomization are available 24/7.

4.15.b Data Analysis

The data analysis will begin by describing the baseline characteristics of the population. Summary statistics, such as means, standard deviations and frequencies will be generated. Graphical techniques, such as scatter plots and box plots will be used to evaluate the distribution of the baseline characteristics.

The balance of the baseline characteristics across treatment group will be compared. For discrete characteristics a chi-square tests or Fisher's exact test will be used to compare the proportions across treatment group. For continuous measures, either t-tests or Wilcoxon tests will be used to compare the characteristics across treatment group.

Aim 1, Hypothesis 1: Administration of amantadine after cardiac arrest will decrease time to awakening when compared to placebo during the 7 days of treatment.

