Kaplan-Meier curves will be generated for time-to-awakening for each treatment group and a log-rank statistic will be used to compare the cumulative probability of awakening across treatment groups. Those participants who are not awake by treatment day 7 will be considered censored observations. A Cox proportional hazards regression model will be used to compare time-to-awakening by treatment group controlling for baseline characteristics that are not balanced through random assignment and stratification variables. The assumptions of the Cox proportional hazards model will be evaluated (proportionality of the hazards model) and if violated, a split analysis will be conducted.

Aim 1, Hypothesis 2: A larger proportion of subjects will awaken during the first 7 days of treatment after administration of amantadine when compared to placebo.

A chi-square test will be used to compare the proportion of participants that are awake at day 7 between the two treatment groups. Logistic regression model will be used to compare the proportions by treatment group controlling for baseline characteristics that are not balanced through random assignment and stratification variables.

Aim 2: Determine if the number of serious adverse events differ between subjects randomized to amantadine and subjects randomized to placebo.

It is anticipated that given the severe critical state of those enrolled in the study, each study participant will have multiple serious adverse events. A t-test (or Wilcoxon test) will be used to compare the means number of serious adverse events that occurred during the 7 days after treatment initiation. A regression model will be used to compare the means after controlling for baseline characteristics that are not balanced through random assignment and stratification variables. The type of regression model will depend in the distribution of the number of serious adverse events and could be a linear regression model, negative binomial model, or Poisson model.

4.15.c Sample Size

The sample size calculations are based on the analysis approach for the primary hypothesis (Aim 1, Hypothesis 1) with a type I error rate of 0.05, a two-sided alternative hypothesis, and 80% power. Based on these assumptions, a sample of 120 (60 per treatment group) will be sufficient to detect a difference of awakening of 30% in the control group and 50% in the active treatment group.

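### Section 4.1 makes awakening during the hospital stay primary, but the hypothesis 4.15.c calls primary stops at treatment day 7, and nothing in 4.15 tests the 4.1 outcome

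*Combined protocol and SAP*

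**What the plan says.** Section 4.1 sets the primary outcome and gives it a window: "The primary outcome will be the rate of awakening (defined as following commands) during hospitalization". Section 4.12 again calls the rate of awakening primary and describes it as short-term, but states no window.

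Section 4.15.c says that the sample size is "based on the analysis approach for the primary hypothesis (Aim 1, Hypothesis 1". Section 4.15.b words that hypothesis as amantadine "will decrease time to awakening when compared to placebo during the 7 days of treatment". Its analysis is by Kaplan-Meier curves, where "a log-rank statistic will be used to compare the cumulative probability of awakening across treatment groups", with a Cox model for adjustment. The cut-off is explicit: "Those participants who are not awake by treatment day 7 will be considered censored observations".

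Hypothesis 2 is that "A larger proportion of subjects will awaken during the first 7 days of treatment", and its chi-square test is to "compare the proportion of participants that are awake at day 7". Aim 2 counts serious adverse events over the 7 days after treatment starts.

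Section 4.15.c states that 120 patients suffice to "detect a difference of awakening of 30% in the control group and 50% in the active treatment group". It attaches no time window to either rate.

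**The concern.** Two parts of the plan each name something as primary, and the two run over different periods. If the analyst follows 4.15 as written, the outcome declared in 4.1 is never tested. If the analyst follows 4.1, the test has to be written later, possibly after outcome data have been seen. A report built on either window could cite the plan in support.

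The windows classify some patients differently. Someone who first follows commands after treatment day 7 but before discharge is a success under 4.1, a censored observation under Hypothesis 1 and a non-awakener under Hypothesis 2. Section 4.12 itself notes that later withdrawal of support may raise the rate of awakening, so the length of the window is not a neutral detail.

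**Working it through.** **Step 1. The definitions side by side.**

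| Place | Role | Measure | Window | Test |
|---|---|---|---|---|
| 4.1 | primary outcome | rate of awakening | hospital stay | none given |
| 4.12 | primary outcome | rate of awakening | none stated | none given |
| 4.15.b, Hypothesis 1 | primary hypothesis (per 4.15.c) | time to awakening | 7 days of treatment | log-rank, Cox |
| 4.15.b, Hypothesis 2 | not labelled | proportion awake | first 7 days, or at day 7 | chi-square, logistic |
| 4.15.b, Aim 2 | safety | count of serious adverse events | 7 days | t-test or Wilcoxon, regression |
| 4.15.c | planning rates | 30% vs 50% | none stated | that of Hypothesis 1 |

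No row pairs the hospital stay with a test. The two windows would coincide only if every stay ended by treatment day 7, and no passage says so.

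**Step 2. Does the plan's own sample size show which window was meant?** The inputs from 4.15.c are 30% vs 50%, two-sided 0.05, 80% power and 60 per arm.

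- Log-rank: hazard ratio = ln(1 − 0.50)/ln(1 − 0.30) = 1.943. Events (Schoenfeld) = 4(1.960 + 0.842)²/(ln 1.943)², which rounds up to 72. With mean awakening (0.30 + 0.50)/2 = 0.40, N = 72/0.40 = 180.
- Chi-square: n per arm = [1.960√(2 × 0.40 × 0.60) + 0.842√(0.30 × 0.70 + 0.50 × 0.50)]²/0.20² = 93, so N = 186.
- At 120 patients, 60 × 0.30 + 60 × 0.50 = 48 events are expected. Power is 0.63 by log-rank and 0.61 by chi-square.

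The stated 120 is not reproduced by either test, so it does not reveal which outcome the rates belong to. That shortfall is a separate matter and carries no weight here.

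**Step 3. How many patients would be classified differently?** Assume that 30% and 50% are day-7 rates, and let L be the share of those not awake at day 7 who awaken before discharge. The documents give no value for L, so I take 2% to 30%. Not awake at day 7: 60 × 0.70 + 60 × 0.50 = 42 + 30 = 72. Late awakeners: 72 × 0.02 = 1.4 to 72 × 0.30 = 21.6 of 120.

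**Step 4. How often would the two analyses disagree?** Simulation of 20,000 trials per scenario, 60 per arm, exponential awakening to day 7, no deaths, uncorrected chi-square, two-sided 0.05, L equal in both arms:

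| L | 0% | 2% | 5% | 10% | 20% | 30% |
|---|---|---|---|---|---|---|
| 7-day log-rank and hospital-stay chi-square disagree on significance | 4.2% | 8.6% | 12.3% | 18.0% | 26.6% | 34.0% |
| Power of hospital-stay chi-square | 0.616 | 0.597 | 0.574 | 0.522 | 0.445 | 0.354 |

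Power of the 7-day log-rank stays at 0.62 to 0.63. The 4.2% at L = 0 comes from the change of test alone. With chi-square in both windows, disagreement over L of 2% to 30% is about 6.5% to 34%, so the choice of test matters only at the low end.

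**Step 5. Is the direction known?** The hospital-stay rate in an arm is p + (1 − p)L.

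- L = 10% control, 20% amantadine: 0.30 + 0.70 × 0.10 = 37% and 0.50 + 0.50 × 0.20 = 60%. Power is 0.73.
- L = 20% control, 10% amantadine: 44% and 55%. Power is 0.24.
- Constant hazard ratio of 1.943, with the longer window raising control awakening to 40% or 50%: log-rank power is 0.74 or 0.82.

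The longer window can gain or lose power, depending on assumptions that the documents do not inform.

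**Step 6. If success were claimed on either window.** With 30% awakening by day 7 in both arms, false positives are 6.4%, 6.9%, 7.2%, 8.4% and 9.0% for L of 2%, 5%, 10%, 20% and 30%. The fair comparator is not 5.0%: with no late awakening, taking the better of the two tests already gives 5.2% to 5.7%.

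**The case against.** The best defence is that the operative plan is clear. Section 4.15.c names one primary hypothesis, and 4.15.b gives it a test and a censoring day. The rest of the plan fits a 7-day horizon: dosing for up to 7 days in 4.5, the Table 2 exclusion tied to at least one week of supportive care, Hypothesis 2 and Aim 2. Section 4.12 contrasts a short-term outcome with long-term function, so the window in 4.1 may be loose shorthand for in-hospital.

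Much of this stands. A reader might infer that the trial has no defined primary analysis, and that would be wrong, because 4.15 defines one. It remains true that 4.1 declares a different outcome as primary. The shorthand reading is possible, but no passage compels it.

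A reader might also infer that the 30% and 50% are day-7 rates, because 4.15.c ties the calculation to Hypothesis 1, and hence that the 4.1 outcome has no planning rates. The text does not support this. The rates carry no window and could be hospital-stay rates, in which case Hypothesis 1 would be the one without them. Section 3, which the plan cites, is not in the text available and may give their source. That could settle the rates but would not remove the conflict between 4.1 and 4.15.

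The difference between a rate and a time to event is the weaker part of the conflict, since 4.15.b describes the log-rank as comparing cumulative probabilities of awakening. The point rests on the window.

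Finally, the sizes are hypothetical. Deaths are ignored, although 4.12 reports persistent coma as the commonest reason for withdrawal of care (56%), and death or withdrawal before awakening would shrink the late group.

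**Conclusion.** Wrong as written. The declared primary outcome and the hypothesis named primary cover different periods, and the declared outcome has no test. This follows from the text alone and does not depend on the simulation.

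The size is illustrative only. It rests on an assumed equal late-awakening share of 2% to 30%, no deaths, and 30% and 50% read as day-7 rates. Two stronger readings should be resisted. One is that the plan inflates the type I error: the 6% to 9% in step 6, against roughly 5% to 6% with no late awakening, bounds a misuse that no passage plans. The other is that the hospital-stay outcome necessarily loses power: step 5 shows that it may go either way.

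**What to change.** State one primary outcome, one window and one test, in the same words, in 4.1, 4.12 and 4.15, before any unblinded outcome data are seen.

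The least change is to align 4.1 and 4.12 with Hypothesis 1:

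- Make the primary outcome time to first following commands through treatment day 7, compared by log-rank.
- Label Hypothesis 2 secondary. Its statement and its test should also agree on whether awakening at any time through day 7 or status at day 7 is meant.
- Make awakening during hospitalization a secondary outcome with its own analysis.
- State the window of the 30% and 50% in 4.15.c.

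The cost is mostly wording. Awakenings after day 7 would no longer count toward the primary result, and the sponsor gives up choosing the window later. The hospital-stay secondary outcome needs the daily examinations of 4.13, which have no stated end, to run to discharge.

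If the sponsor keeps the 4.1 outcome as primary, 4.15.b must give it a test and 4.15.c must be based on hospital-stay rates. The sample size then depends on what those rates are. If 30% and 50% are already hospital-stay rates, the chi-square formula in step 2 gives 93 per arm for 80% power. If they are day-7 rates, the same formula gives 98 to 194 per arm for equal late awakening of 2% to 30%, 73 per arm at 37% vs 60%, and 324 per arm at 44% vs 55%. Whichever outcome is chosen, power in 4.15.c has to be restated for it.

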4.4 Randomization

After informed consent, subjects will be randomly assigned to either amantadine or placebo. For intention-to-treat analysis, subjects will be considered to be randomized as soon as an assignment is made. For per-protocol analyses, subjects will be considered to be randomized after receiving the first dose of study medication. The Investigational Drug Service (IDS) at the University of Pittsburgh will prepare and

dispense study drug and maintain the block randomization list. At randomization, subjects will be stratified by PCAC strata and presence of early malignant patterns on EEG recording (these EEG patterns must have stopped by time of randomization, because continued malignant EEG is an exclusion). Both of these have been associated with outcome. [2, 16, 32, 3.C.1.b]

Table 2. Inclusion and Exclusion Criteria

Inclusion Criteria	Exclusion Criteria
Non-traumatic cardiac arrest	Written do not attempt resuscitation (DNAR) reported to providers before randomization
Age 18 years or more	Known prisoner or pregnancy
Defibrillation and/or chest compressions by healthcare providers	Lack of motor response to pain and absent N2O response on SSEP prior to randomization.
Return of spontaneous circulation	Initial CT demonstrating brain edema (defined as grey white ratio <1.2)
	Presence of malignant pattern on EEG at time of randomization.
	Next of kin unwilling to provide supportive care for at least one week after enrollment.
	Creatinine clearance <50mL/min
	Presently using other dopaminergic agent

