4.14 Prognostic Evaluation

Prior literature has demonstrated that individual physical exam or test findings are insufficient to preclude a good outcome. Therefore, no single finding will result in cessation of support. [7, 37, 38] A multimodal workup will be employed to predict neurologic outcome. This includes clinical examination, continuous EEG monitoring, computerized tomography, somatosensory evoked potentials, and magnetic resonance imaging. [Figure 4] The clinical examination is described in Table 4. Continuous EEG monitoring is described above.

Table 4. Clinical Examination of Comatose Post-Arrest Patients

Reflex	Method to Elicit	Potential Responses
Pupil Response	Light stimulus into each pupil for 5 seconds in a darkened room. A positive response will consist of any pupillary response to the light stimulus.	0- Absent 1- Present
Corneal Response	3 drops of sterile saline will be dropped onto the cornea from a distance of 5cm. If this does not elicit a corneal response, sterile gauze will gently be used to stimulate the cornea. Any blink response will be considered a positive response.	0- Absent 1- Present
Gag Response	A Yankauer catheter will be used to suction the posterior pharynx and tonsilar pillars. Gagging will be considered a positive response.	0- Absent 1- Present
Motor Response	Supraorbital pressure, pectoral pinch, and stimulation of the nailbeds with pressure exerted by forceps will be used to elicit a response. The best motor response will be recorded.	0- No response or myoclonus 1- Decorticate posturing 2- Decerebrate posturing or withdraw to pain 3- Localization 4- Following commands

Figure 4. Timeline and testing for neurologic prognostication. EEG- electroencephalogram; SSEP- somatosensory evoked potential; MRI- magnetic resonance imaging.

4.14.a Computerized tomography of the brain- Loss of grey-white differentiation (gray-white ratio of Hounsfield Units <1.2) on initial CT of the brain predicts survival and neurologic outcome following cardiac arrest. [39-41] Subjects with a grey-white ratio <1.2 will be excluded from the study.

4.14.b Somatosensory evoked potentials- Subjects without a motor response to painful stimuli (GCS Motor=1) at 72 hours following cardiac arrest will have SSEP's obtained as part of the standard protocol. A lack of N20 response bilaterally remains predictive for a poor neurologic outcome following cardiac arrest. [42]

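### Patients who could follow no command before the arrest are eligible but cannot reach the primary endpoint, which mildly dilutes the effect; one exclusion line would close the gap

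*Combined protocol and SAP*

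**What the plan says.** Section 4.1 gives the endpoint and its only definition: "The primary outcome will be the rate of awakening (defined as following commands) during hospitalization". Table 4 (section 4.14) records the same event as the highest motor score, "4- Following commands". Neither place makes the event relative to the patient's own baseline.

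The target population in section 4.1 is "patients resuscitated from cardiac arrest who remain comatose at hospital day 3". Section 4.3 refers to Table 2 for eligibility. Table 2 has four inclusion criteria: non-traumatic arrest, adult age, resuscitation by healthcare providers, and return of circulation. It has eight exclusion criteria, of which three are neurologic findings:

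- "Lack of motor response to pain and absent N2O response on SSEP prior to randomization"
- "Initial CT demonstrating brain edema (defined as grey white ratio <1.2"
- "Presence of malignant pattern on EEG at time of randomization"

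All three describe the brain after the arrest. The first study examination (section 4.13) takes place on hospital arrival, so it cannot show earlier ability. Randomization is stratified only by PCAC category and, within PCAC II, by malignant EEG (section 4.15.a).

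In section 4.15.b, patients not awake by treatment day 7 are censored in the time-to-awakening analysis. The chi-square test compares the proportions awake at day 7. Section 4.15.c plans 60 per arm for 30% against 50% awakening, with two-sided alpha of 0.05 and 80% power.

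**The concern.** The endpoint assumes that every enrolled patient could follow a command before the arrest, and nothing in Table 2 ensures it. For a patient who could not, the best recovery possible is a return to a state that the endpoint does not count. The result is then fixed in advance under either treatment.

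At stake is sensitivity. Patients who cannot have the event add non-events to both arms, reduce the absolute difference in awakening and lower power. Some real recoveries would also go uncounted in the primary outcome.

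**Working it through.** **Can such a patient enter, and how is the patient scored?**

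1. Entry: none of the twelve Table 2 criteria asks about function before the arrest. The exclusions for a written DNAR and for next of kin unwilling to support care for a week concern wishes, not ability. They may remove some of these patients but need not remove all.
2. Scoring: the motor score of 4 requires following commands. A patient who could follow none before the arrest stays below 4 on return to baseline.
3. Analysis: that patient is censored at day 7 in the log-rank and Cox analyses, and is a non-event in the chi-square and logistic analyses.

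**The plan's own figure**

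Inputs from section 4.15.c: p1 = 0.30, p2 = 0.50, two-sided alpha 0.05, 80% power, 60 per arm.

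Two proportions, pooled variance under the null, mean rate 0.40:

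n per arm = [1.96 × √(2 × 0.40 × 0.60) + 0.842 × √(0.30 × 0.70 + 0.50 × 0.50)]² / 0.20² = 93, or 186 in total.

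Log-rank (Schoenfeld), hazard ratio = ln(0.5)/ln(0.7) = 1.943: 72 events, and 72/0.40 = 180 patients.

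The stated 120 is not reproduced by either method. Power at 60 per arm is:

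- Two proportions: Φ{[0.20 − 1.96 × √(0.48/60)] / √(0.46/60)} = Φ(0.282) = 61.1%.
- Log-rank with 60 × (0.30 + 0.50) = 48 expected events: Φ{(√48/2) × ln 1.943 − 1.96} = 63.4%.

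That shortfall is a separate matter. It is used here only as the baseline for the comparison.

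**Dilution**

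Let q be the share of enrolled patients who could follow no command before the arrest. The documents do not give q; 1% to 10% is an assumed range. If 30% and 50% apply to the other patients, the observed rates become 0.30(1 − q) and 0.50(1 − q).

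| q | Such patients in 120 | Rates | Difference (points) | Power, two proportions | Power, log-rank |
|---|---|---|---|---|---|
| 0 | 0 | 30.0% vs 50.0% | 20.0 | 61.1% | 63.4% |
| 1% | 1.2 | 29.7% vs 49.5% | 19.8 | 60.4% | 62.6% |
| 5% | 6 | 28.5% vs 47.5% | 19.0 | 57.4% | 59.6% |
| 10% | 12 | 27.0% vs 45.0% | 18.0 | 53.8% | 55.9% |

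Example at q = 5%: the mean rate is 0.38, and Φ{[0.19 − 1.96 × √(2 × 0.38 × 0.62/60)] / √((0.285 × 0.715 + 0.475 × 0.525)/60)} = Φ(0.188) = 57.4%.

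Over the range the cost is (61.1 − 53.8)/10, or about 0.7 points of power per 1% of such patients.

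**Does exclusion pay if the places are not refilled?**

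Exclusion restores 30% against 50% but leaves 60(1 − q) per arm.

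- q = 5%, 57 per arm: Φ{[0.20 − 1.96 × √(0.48/57)] / √(0.46/57)} = 58.9%, against 57.4% if they stay.
- q = 10%, 54 per arm: 56.5%, against 53.8% if they stay.

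Power is slightly higher with exclusion even without replacement.

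**The case against.** The strongest case against is that the affected group is narrow and its size unknown. Deafness does not put a patient in it: Table 4 does not say that commands must be spoken, so a written or gestured command would count. Dementia does not by itself prevent following a simple command. Only patients unable to follow any command in any form are affected. The DNAR and next-of-kin criteria, with consent by proxy, may remove some of them. This stands, and at q = 1% the loss is under one point of power.

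The dilution also rests on a condition. If 30% and 50% were meant for everyone Table 2 admits, such patients are already in those rates and the calculated loss does not arise. The text provided does not show where the 30% comes from. This stands too.

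Three stronger readings are tempting, and the documents do not support them:

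- **The comparison is biased.** Allocation is randomized and blinded, and such patients are expected equally in both arms. The type I error is unaffected; a chance imbalance is possible, as with any unstratified factor.
- **These patients are recorded as being in persistent coma.** The plan censors them or counts them as not awake, and Table 4 has graded motor scores below 4. The record that they do not follow commands would be accurate.
- **They contribute nothing to the trial.** They still count for serious adverse events under Aim 2 and, if on amantadine, for the plasma-level data in section 4.8.

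Finally, section 4.12 defends awakening as a precondition of good neurologic outcome, and a uniform threshold has value. That supports keeping the definition. It does not explain enrolling patients who could not meet it before the arrest.

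**Conclusion.** The gap is real and small. Following commands is the only definition of awakening, eligibility says nothing about that ability before the arrest, and no later step in the plan catches the mismatch. The consequence is dilution of the primary comparison. Its size is conditional: about 0.7 points of power per 1% of such patients, if the planned rates describe patients able to follow commands, and no loss against plan if those rates already include the others. The documents supply neither q nor the basis of the rates. This is a cheap improvement to the design. It does not threaten the validity of the comparison, and it is minor beside the separate sample-size shortfall.

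**What to change.** Add one line to the Table 2 exclusions: *Known inability to follow any command (spoken, written or gestured) before the cardiac arrest.* Ascertain it by one question to the proxy who is already being approached for consent under section 4.2. Naming all three forms keeps deaf patients, and patients with milder cognitive impairment, eligible.

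No new test or visit is needed. The costs are a small loss of eligible patients, the loss of their adverse-event and plasma-level data, and a slightly narrower population.
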